Study Title: STORY: A pilot randomized controlled trial using Storytelling To prevent Obesity and encourage Responsive feeding practices in Young children

Principal Investigator: [name]

Co-investigator(s): [name], [name], [name], [name]

Sponsor or funding source: Center for Prevention Science in Child and Family Health

Background, Rationale and Context

Parents commonly exert controlling feeding practices in which they pressure their child to eat or restrict the types of foods their child eats. Even when parents pressure their child to eat healthy foods and restrict unhealthy foods, this has been paradoxically associated with lower fruit and vegetable intake and increased weight gain over time. Many parents fail to establish structure around feeding, allowing their child to eat when, where, and what foods they prefer and having few meal routines. This lack of structure has been associated with increased risk of overweight/obesity. While previous studies have shown that parent education interventions are effective in improving child feeding practices, there remain barriers, such as time and provider comfort level, to implementing these interventions in clinical and community settings. It is unclear whether aspects of intervention delivery – notably who delivers the intervention and the setting in which it is delivered – impact intervention effectiveness. Narrative persuasion has demonstrated the power of storytelling to influence viewers' attitudes and beliefs, however, research by health interventionists has to date largely failed to integrate storytelling as an approach to health behavior change. **To address these gaps, our goal is to develop a novel storytelling video series to educate parents about healthy parent feeding practices and to assess feasibility and acceptability of the intervention through a pilot randomized controlled trial in diverse clinical and community settings.**

Objectives

Conduct a pilot randomized trial to assess feasibility and acceptability of STORY. We will recruit 60 parents (20 per intervention mechanism + 20 controls) of healthy 2- to 4-year-old children from pediatric primary care offices. Parents will complete a questionnaire and dyads' heights and weights will be measured. Families will be randomized to the control group or **1 of 2 intervention delivery approaches (IA):**

- IA 1. Online-only video series introduced by general pediatrician at primary care office

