- IA 2. Weekly classes with video viewing and group discussion led by Second Harvest Food Bank's Nutrition Services team, a community organization focused on providing evidence-based nutrition education

Parents will be given a handout (controls), links to the videos to watch independently (IA 1), or information on how they will be contacted to schedule their intervention sessions (IAs 2). After 2 videos/sessions, all parents will complete a written survey assessing their experience with the intervention and any changes made at home; the written survey will reassess baseline measures. Intervention parents will also complete a semi-structured interview to assess the family's experience with the STORY trial.

Sub aim 2a: Feasibility: number of parents approached, number of parents consented

Sub aim 2b: Adherence: number of parents who complete videos or sessions

Sub aim 2c: Acceptability to parents and providers

Aim 3: Concurrently with Aim 2, we will obtain pilot data to estimate variances (means, SD) of measures to be utilized in the larger study. We will utilize data from the pilot trial described in Aim 2. Measures include anthropometrics, parent controlling feeding practices,

child self-regulation of eating, and family mealtime practices at baseline and after STORY intervention delivery.

Methods and Measures

Design

In a pilot randomized controlled trial we will recruit parents of healthy 2–4-year-old children from three primary care offices with diverse patient populations. Participants will complete baseline questionnaires and be randomized to one of three groups. The control group will receive an educational handout at the baseline visit. The intervention will be delivered through one of two mechanisms: (1) links provided to online-only video series (2 videos) by general pediatrician at primary care office, and (2) 2 weekly group sessions with video viewing and group discussion led by Second Harvest Food Bank's Nutrition Services team, a community organization focused on providing evidence-based nutrition education. The Nutrition Services team has experience leading group classes from cooking classes and summer meal site activities for children to food demonstrations and community garden workshops.

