We will assess the feasibility and acceptability of the intervention and delivery mechanisms to intervention participants and providers. After completion of the 2-week intervention we will assess the change in all participants' parental pressure to eat, child self-regulation of eating, and family mealtime practices.

Setting

We will recruit participants from academic pediatric primary care practices, including Winston East Pediatrics, The Downtown Health Plaza, and Ford Simpson Lively and Rice Pediatrics, three clinics affiliated with Atrium Health Wake Forest Baptist (AHWFB). One child per family will be recruited; if more than one is eligible, we will enroll the youngest eligible child.

Subjects selection criteria

• Inclusion Criteria

Parent participants will be included if the parent is at least 18 years old and can read and write English and if the child has no medical conditions that affect development, feeding, or growth.

Provider participants will be included if the provider leads a discussion group or refers patients into the study.

• Sample Size

60 parent participants and 60 child participants will be recruited.

20 provider participants will be recruited.

Interventions and Interactions

All participants will complete baseline questionnaires at the time of recruitment and all participants will complete follow-up questionnaires, either one month after recruitment (for controls and IA 1 participants) or after completion of their intervention (IA 2 participants). The IA 1 participants will receive an email reminder stating, "You are receiving this email because you signed up to participate in a short study during your child's visit with their doctor. This is a reminder to watch the two videos (links provided below) if you have not already done so and please know that you will receive a link to a second survey soon. Once the second survey is

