completed, you will receive another \$30 gift card.” Additionally, IA 1 participants’ email will include personalized links to videos to track those who watched the videos. Control, IA 1, and IA 2 participant groups will receive an email with the following text, “You are receiving this email because you signed up to participate in a short study during your child’s visit with their doctor. You completed the first survey on a tablet during your child’s visit. Here is a link to the follow-up survey. Once we have been notified that you have completed the survey we will mail you a \$30 gift card as a thank you for completing the survey. If your address has changed since your child’s last doctor’s appointment, please let us know where you would like us to mail the gift card.”

After 2 sessions, intervention parents will complete a semi-structured interview (IA 1-2). The semi-structured interview will use open-ended questions to assess the family’s experience with the intervention. An interview guide will be developed, and we will test interview questions for clarity, comprehension, and face-validity via cognitive interviews with volunteers. Semi-structured interviews were chosen to allow study staff to obtain clarification, probe for detail, and allow new topics to emerge.

Links to the videos will be provided via individualized QR codes to participants. The videos can also be found at the following link:

<https://youtu.be/IFS5V4lcwyA>

<https://youtu.be/GWodDTyzepE>

Outcome Measure(s)

We will assess feasibility by evaluating the number of families who are approached for participation at primary care offices and the number consented and randomized.

We will assess adherence by evaluating the number of videos viewed (tracked through REDCap in IA 1) or sessions attended (IA 2) by each participant. Based on our experience in previous trials and what is widely accepted in behavioral interventions, we will define successful adherence to the intervention as completing 2 out of the 2 sessions (100%).

We will assess retention by evaluating the number of participants who complete the final study visit.

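### Does counting retention by an undescribed last visit, and listing anthropometrics in Aim 3 with no follow-up measurement, leave the pilot's results undefined?

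*Combined protocol and SAP*

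**What the plan says.** Outcome Measure(s) defines retention in one sentence: "We will assess retention by evaluating the number of participants who complete the final study visit". The protocol does not say when or where that visit takes place or what it contains. The only other study visit it names is the baseline one.

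Interventions and Interactions describes follow-up for everyone as a questionnaire, timed "either one month after recruitment (for controls and IA 1 participants) or after completion of their intervention (IA 2 participants". The email that goes to all three groups says "Here is a link to the follow-up survey", and the gift card is then mailed. A further contact exists for two arms only: "After 2 sessions, intervention parents will complete a semi-structured interview (IA 1-2".

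On anthropometrics, the Objectives place measurement before allocation: "heights and weights will be measured. Families will be randomized to the control group". They give the later reassessment to the questionnaire: "the written survey will reassess baseline measures". Aim 3 then gives a list that opens "Measures include anthropometrics, parent controlling feeding practices" and closes "child self-regulation of eating, and family mealtime practices at baseline and after STORY intervention delivery". The Survey Measures text says that study staff take height and weight, without a time point.

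**The concern.** Retention is a listed outcome measure of a feasibility pilot, so the event being counted ought to be identifiable. The text speaks of a visit, the follow-up it describes is remote, and two of the three arms have an additional contact. If someone took the visit to mean each arm's last contact, intervention parents would have to complete an interview that controls are never offered, and the arms would be counted on different events.

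The Aim 3 list raises a similar doubt. Read naturally, its closing time points cover every item, including anthropometrics. Height and weight are taken by staff, so a survey cannot supply them. No in-person contact after baseline is described for the control and IA 1 dyads, and the IA 2 sessions include no stated measurement. The health-record link under Informed Consent concerns the child only and names no fields or dates. On that reading, the aim would promise post-intervention means and SDs that the described schedule cannot deliver.

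**Working it through.** **Inputs.** From Objectives: 20 parents in each of two intervention arms and 20 controls. The stated total is reproduced: 2 × 20 + 20 = 60. The documents give no expected retention and no retention target.

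**Retention: the possible readings compared.**

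| Reading of the visit | Who can be counted | Maximum retention |
|---|---|---|
| Follow-up survey | all three arms | 60/60 = 100% |
| Interview | IA 1 and IA 2 only | 40/60 = 66.7%; control 0/20 |
| Each arm's last contact | survey for controls, survey and interview for IA 1 and IA 2 | 60/60, but on unequal events |
| In-person visit | none described after baseline for controls; mode of the IA 1 interview not stated | not computable |

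Under the last-contact reading, each intervention parent who completes the survey but not the interview lowers that arm's figure by 1/20 = 5 percentage points and the overall figure by 1/60 = 1.7 points. Controls cannot be moved in this way. The documents give no basis for saying how many such parents there would be.

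**Which reading fits the text.** The definition counts participants without restricting the arm. The Objectives, the Interventions and Interactions text and the common email all give the survey to every arm. The interview reading fails because it sets control retention to zero by design. Nothing in the protocol suggests the last-contact reading. The survey is the only described event that satisfies the definition in all arms.

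**What depends on it.** Retention is to be reported as a count. It does not appear in sub-aims 2a to 2c, which cover feasibility, adherence and acceptability. No progression criterion and no between-arm retention comparison is planned.

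**Anthropometrics: the places side by side.**

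- Objectives: height and weight are taken with the baseline questionnaire, before randomization.
- Aim 3: anthropometrics comes first in a list whose last item carries the baseline and post-intervention time points.
- Design: the change assessed after the two-week intervention covers pressure to eat, child self-regulation and mealtime practices. Anthropometrics is absent.
- Analytical Plan: the regression outcomes are change in controlling feeding practices, self-regulation and mealtime structure. Parent BMI enters only as a covariate.

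The two places that say specifically what is assessed or modelled as change agree with each other, and both fit baseline-only anthropometrics.

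**Precision.** Confidence intervals around an assumed retention proportion would describe sampling error at n = 20 or n = 60. At a given proportion they are the same whichever event is counted, so they do not measure this ambiguity.

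**The case for a change.** The strongest case for a change is that both observations are accurate and the repair is cheap. A pilot should name the event, window and denominator of each outcome it lists, and a few sentences would do it. For Aim 3, the natural grammar does attach both time points to anthropometrics, so the baseline-only reading has to be inferred from other sections. There is also an IA 2 wrinkle: that arm's survey is timed from completion of the intervention, which leaves a parent who stops early without an explicit date.

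The factual core stands: the visit is undescribed and no follow-up measurement is scheduled. The claimed consequence does not. Unequal events across arms arise only under a reading the text does not suggest, and no comparison of arms on retention is planned. The IA 2 timing is a separate question, and most of it is answered already, since all participants are to complete the follow-up questionnaire and all three groups are emailed the link. A tidier sentence would be harmless, but it would record what analysts would do anyway.

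**Conclusion.** The concern does not call for a change. On retention, one loose word stands where the survey is evidently meant. On anthropometrics, one list in Aim 3 is ambiguous, and the Design and Analytical Plan sections point to its narrower reading.

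The gap between the extreme retention readings is large on paper, at most 40/60 against 60/60, but the lower figure comes from a reading that excludes every control by construction. No planned regression outcome is affected by either point, and no decision rule turns on them.

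This rests on two assumptions: that analysts will count follow-up surveys over all randomized parents, the only described event open to every arm, and that no further measurement visit was intended beyond what the protocol describes. If one was intended, Aim 3 and the described schedule would need to be reconciled, but the documents give no sign of it outside that one list and the single mention of a visit.

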We will assess family mealtime practices with the Family Meal Frequency Questionnaire which assesses how many times a week the family eats dinner together, both at home and at a restaurant.⁴² We will also use the Structure of Family Meals subscale of the Meals in our Household Questionnaire (10 items), which assesses whether the meal is eaten in the kitchen/dining room, whether members of the family ate the same food, and whether the meal is eaten at a regular time (never, rarely, sometimes, often, or always. This measure has been validated in preschool and school-aged children.⁴³

Demographic questions will include household income and food insecurity; parents' education; and child's sex, race, ethnicity, insurance status, number of siblings, birth order, and daycare/school attendance. Parent and child weight and height will be measured by study staff. Number of siblings and birth order,⁴⁴ food insecurity,⁴⁵ and child weight status⁴⁶ have all previously been associated with parent feeding practices.

Analytical Plan

Statistical Analysis of Pilot Data: We will use this pilot data to estimate variances (means, SD) of measures to be utilized in the larger future effectiveness trial. In the analysis of this pilot data, we will use separate regression models assessing differences between each type of intervention and the control group for our outcomes of change in controlling feeding practices, child self-regulation of eating, and family mealtime structure. We will use intention to treat analyses and will adjust for child race/ethnicity, age, and sex; number of siblings; parent BMI; household income and food insecurity; and baseline feeding practice/self-regulation/mealtime structure.

Human Subjects Protection

Subject Recruitment Methods

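### IA 2 is delivered in group classes, but the planned regressions have no term for class, so the IA 2 versus control standard error is too small if the class ICC is above 0

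*Combined protocol and SAP*

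**What the plan says.** Under Objectives, "Families will be randomized to the control group" or to one of two delivery approaches, with 20 parents in each of the three arms. Controls receive a handout. IA 1 is an "Online-only video series introduced by general pediatrician at primary care office", which parents watch on their own. IA 2, under Design, consists of "2 weekly group sessions with video viewing and group discussion led by Second Harvest" staff.

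The Analytical Plan states that "we will use separate regression models assessing differences between each type of intervention and the control group" for the change outcomes. It continues: "We will use intention to treat analyses and will adjust for child race/ethnicity, age, and sex; number of siblings; parent BMI; household income", and also for food insecurity and the baseline value of the outcome. The same section says: "We will use this pilot data to estimate variances (means, SD) of measures to be utilized in the larger future effectiveness trial".

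Outcome Measure(s) provides for counting "sessions attended (IA 2) by each participant". Its fidelity paragraph has sessions audio recorded and a checklist completed for each one. Nowhere do the documents mention class, facilitator effect, ICC, random effects or robust standard errors in the analysis. They give neither the number nor the size of the classes, and they do not say that a session or facilitator identifier is attached to a parent's outcome data.

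**The concern.** Individual randomisation makes families independent at entry, but IA 2 then puts some of them in the same room with the same discussion and facilitator. Outcomes within a class may become alike, in that arm only and after randomisation. An ordinary regression without a class term counts 20 IA 2 parents as 20 independent observations. If the class ICC is positive they carry less information than that, and the SE, interval and p value for IA 2 versus control look more precise than the data support.

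There is a second consequence. The pilot is meant to supply planning values for a larger trial, and means and SDs without class numbers and sizes omit what is needed to size a group-delivered arm.

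IA 1 has no class effect. Its parents may share an introducing pediatrician, so nothing here implies that IA 1 observations are fully independent.

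**Working it through.** **Inputs from the documents.** 20 IA 2 parents and 20 controls, randomised individually; classes in IA 2 only; covariates as listed in the Analytical Plan. The allocation adds up (2 × 20 + 20 = 60). No alpha, power, effect size or SD is given, so there is no power calculation to reproduce.

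**Assumptions, not in the documents.** Class size m from 2 to 10, ICC from 0.01 to 0.10, equal total variance in both arms, nominal 95% interval.

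**Formulas** (n2 and nc are the numbers analysed in IA 2 and control):

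- Design effect in IA 2: DE = 1 + (m − 1) × ICC
- SE multiplier: M = sqrt[(DE/n2 + 1/nc) / (1/n2 + 1/nc)]
- Expected shrinkage of the pooled variance: b = 1 − (m − 1) × ICC / (n2 + nc − 2)
- True SE over reported SE: R = M / sqrt(b)
- Coverage = 2T(t/R) − 1, where T is the t distribution function on n2 + nc − 2 df and t its 97.5% point

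**Example, classes of 5 at ICC 0.05, 20 v 20.** DE = 1 + 4 × 0.05 = 1.20. M = sqrt[(1.20 + 1)/2] = 1.049. b = 1 − 0.20/38 = 0.995. R = 1.049/sqrt(0.995) = 1.052. Coverage is 93.8%.

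**20 v 20, no covariates:**

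| Class size | ICC | M | R | Coverage |
|---|---|---|---|---|
| 2 | 0.05 | 1.012 | 1.013 | 94.7% |
| 3 | 0.05 | 1.025 | 1.026 | 94.4% |
| 5 | 0.01 | 1.010 | 1.011 | 94.8% |
| 5 | 0.05 | 1.049 | 1.052 | 93.8% |
| 5 | 0.10 | 1.095 | 1.101 | 92.6% |
| 10 | 0.01 | 1.022 | 1.024 | 94.5% |
| 10 | 0.05 | 1.107 | 1.113 | 92.3% |
| 10 | 0.10 | 1.204 | 1.219 | 89.5% |

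A simulated two-sample t-test (100,000 runs per setting) gave type I error of 6.2% and 7.5% for classes of 5 at ICC 0.05 and 0.10, and 7.6% and 10.5% for classes of 10, against a nominal 5%. This agrees with the table to about 0.1 percentage points.

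**With covariates, closer to the planned model.** Ten columns: three for race/ethnicity and one each for age, sex, siblings, parent BMI, income, food insecurity and baseline score. They were simulated as unrelated to class, with 100,000 runs per setting.

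| Class size | ICC | R | Coverage, uncorrected | Coverage with SE × M at the true ICC |
|---|---|---|---|---|
| 5 | 0.05 | 1.036 | 94.2% | 95.3% |
| 10 | 0.10 | 1.162 | 90.9% | 95.6% |

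**Incomplete follow-up or attendance (assumed numbers).**

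- 14 IA 2 parents analysed in two classes of 7 against 20 controls: at ICC 0.05, M = sqrt[(1.30/14 + 1/20)/(1/14 + 1/20)] = 1.085; at ICC 0.10, M = 1.163.
- All 20 analysed, 6 of whom attended no session and count as classes of one: the weighted class size is (49 + 49 + 6)/20 = 5.2, and M = 1.051 and 1.100.

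**Can the ICC be estimated from this pilot?** The chance that the ANOVA estimate is zero or below is the F distribution function at (1 − ICC)/DE. At a true ICC of 0.05 it is 48% with four classes of 5 and 57% with two classes of 10. The pilot cannot supply a usable ICC.

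**The case against.** The strongest reply is that this matters little here. The trial is about feasibility and acceptability. The documents set no alpha or decision rule that uses this SE, and do not say whether intervals will be reported. The point estimate is unaffected. Class size and ICC are assumed throughout, and nothing in the documents favours the upper end of the range. The planned model is covariate-adjusted, so the smaller adjusted figures are the relevant ones; if class membership follows income or baseline score, the residual ICC would be smaller still. The plan also never says that parents are independent, and per-parent attendance and session recordings may allow class membership to be recovered later.

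Most of this stands as a limit on importance, and it is why the adjusted range leads and the remedy is only a sensitivity analysis. It does not remove the point. The protocol chose to fit between-group regressions, and a regression with no class term assumes independence whether or not it says so. Because class size is not stated, the effect cannot be dismissed as negligible in advance. Session records exist, but nothing says they will be linked to outcomes.

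**Conclusion.** The concern holds. For any class size above 1 and class ICC above 0, the planned analysis understates the SE of IA 2 versus control. From classes of 5 at ICC 0.05 to classes of 10 at ICC 0.10, the understatement corresponds to a true SE 1.04 to 1.16 times the reported one with ten covariates unrelated to class, or 1.05 to 1.22 times without covariates. At the low end of the assumed range it can be ignored. These sizes rest on assumed class sizes and ICCs, so the direction is firmer than the amount. It should be addressed, but it does not threaten the feasibility and acceptability aims.

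**What to change.** 1. Record the session and facilitator for each IA 2 parent in each of the two weeks. State in advance which session defines class if a parent switches.
2. Beside the planned IA 2 versus control estimate, report it with the SE multiplied by M at ICC 0.01, 0.05 and 0.10. Take m as the sum of squared analysed class sizes divided by n2, counting analysed non-attenders as classes of one. Say that this is approximate for covariate-adjusted models and when parents switch sessions, and that it is too low if one facilitator leads several classes and facilitators differ.
3. Report the number and sizes of classes next to the means and SDs, so that a later group-delivered arm can be sized with a design effect over a range of ICCs. Do not carry forward an ICC estimated from this pilot.

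The cost is one or two extra fields per session and no added burden for parents; it is cheapest to do while sessions are being held. The price in precision is an SE about 1% to 20% larger for classes of 5 to 10 (M from 1.010 to 1.204). If the true ICC is 0 this is too wide: coverage is 98.0% for classes of 10 corrected at ICC 0.10. For that reason the corrected SEs should be shown as a range alongside the planned analysis and should not replace it.
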